9.6 FOLLOW-UP VISITS

9.6.1 FOLLOW-UP VISIT ROUTINE PROCEDURES

Prior to the Visit: Reminder Call

A few days before the follow-up visit, it is recommended that the coordinator contact the subject to remind them to bring their unused Refresh Plus vials and, if they are in the warm compress group, their Warm Compress Log.

Also, since dry eye drops and lubricants can affect the endpoint assessments, it is important to remind subjects, on the day of the Follow-up visit, not to use any of these products before the Follow-up visit.

At the Beginning of the Follow-up Visit: Maintaining Masking of Study Personnel

Endpoint assessments performed during the Follow-up visit must be performed by the Masked Assessor (See Section 9.7).

At the beginning of the follow-up visit, the coordinator should remind the subject to not reveal their randomization group to the study personnel who will be performing the follow-up exams.

Order of Procedures During the Follow-Up Visit

Follow-up procedures will be performed per the Study Schedule provided in Table 3 (page 28) and the methods included in Appendix A. Since certain tests/exams can impact the ability to perform other tests/exams, the following tests and exams should be performed in this order:

- 1. Questionnaires
- 2. Manifest refraction and ETDRS Best-corrected visual acuity
- 3. Slit Lamp Exam
- 4. Tear Breakup Time
- 5. Corneal and conjunctival staining score
- 6. Meibomian Gland Secretion Scoring

CONFIDENTIAL Sight Sciences

- 7. IOP
- Assessment of adverse events

The following activities can be performed in any order:

- Medication Use
- Collection of Warm Compress Log
- · Count unused Refresh Plus Vials

At the End of the Follow-Up Visit

At the end of the follow-up visit, provide subjects with a new supply of Refresh Plus vials, if needed. Record how many vials are provided to the subject.

For subjects in the Warm Compress and Lid Massage group, provide them with a new Warm Compress Log for use in the next follow-up period.

9.6.2 6 Month Follow-up Visit: Re-Treatment

Scheduling the 6 Month Visit

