9.7 MASKED ASSESSOR

To reduce potential bias in the study, study staff performing endpoint assessments will be masked as to the subject's treatment arm. In addition, to ensure consistency in performing the endpoint assessments the study staff member who performs the baseline assessments should also perform the follow-up assessments. An alternate Masked Assessor may be appointed to handle scheduling conflicts, but every effort should be made to have the same person performing all endpoint assessments throughout the study. The Masked Assessor should not perform the randomization, inoffice TearCare Treatment, gland expression or the in-office warm compress treatment prior to home use. Masking will be maintained until all subjects at the site have passed the 6-month follow up time.

The following assessments must be performed by Masked Assessor:

- Manifest refraction and BCVA
- Slit lamp exam
- Tear Break-up Time
- Corneal and conjunctival staining
- Meibomian gland secretion scoring
- IOP
- AE assessment

The study coordinator should collect the Warm Compress Log from the subject.

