10.2 LIST OF ANTICIPATED POTENTIAL ADVERSE EVENTS

Anticipated potential adverse events include those that might reasonably be expected to occur in this study because they are associated with dry eye disease, the risk analysis for TearCare System (albeit remote likelihood), study testing methods or potential risks associated with warm compresses and lid massage.

- Burn, erythema, or swelling of the eyelids
- Conjunctival injection (Moderate or severe)
- Conjunctival abrasion
- Corneal abrasion
- Corneal deformation
- Allergic or inflammatory reaction to medical adhesive on the iLid device

- Formation of a chalazion or stye
- Loss in BCVA of 2 lines or greater
- Worsening of dry eye symptom
- Increased discomfort or pain of ocular surface (grittiness, foreign body sensation, etc.)
- Discomfort or pain of eyelids or orbit

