11.5 Possible interactions with concomitant medical treatments

It is anticipated that there will be no interactions with concomitant medical treatments.

11.6 Steps that will be taken to control or mitigate the risks.

The major risks to the subjects and the steps taken to control or mitigate them are described below:

1. Overheating of the eyelids: All TearCare treatments will be done in the investigator's office under direct supervision of the investigator. The device delivers heat to the eyelids at a temperature ranging from 41-45°C. This temperature range was selected because it is both safe for eyelid heating and

effective for melting obstructions in the meibomian glands.^{48,49,50,51} The user can adjust the temperature up or down to a level that is comfortable, and may also shut off the System at any time if it is too uncomfortable or painful. In addition, the TearCare System continuously monitors and regulates the temperature at the tissue-contacting surface of the iLid devices and has been designed to not exceed the maximum allowable temperature.

- 2. Corneal abrasion: If the iLid devices are not positioned properly or come loose during the treatment, there is the potential for a corneal abrasion. To mitigate this, the supervising physician will apply the strips to the subject and will monitor their position during the treatment to ensure they remain in place and secure.
 - In addition, there is the possibility of corneal abrasion or abrasion of the eyelid surface during expression of the meibomian glands. To reduce the chance of abrasion, the forceps have been designed with smooth surfaces (i.e. no rough edges) and only trained users will perform expression.
- Worsening of dry eye symptoms: It is possible that subjects will experience a
 worsening of dry eye symptoms during the study. Subjects will undergo a
 complete eye exam at each visit and if any untoward or worsening signs of
 ocular surface disease are observed, they will be treated appropriately.

In addition to the above, the following mitigation steps have also been taken to reduce the risks in this study:

- The device has been tested to demonstrate that it meets performance and safety specifications, as described in Section 5.1.
- Instructions for Use are provided with each device.
- The clinician using the device will be trained in how to safely and correctly apply and remove the iLid devices, and operate the TearCare System.

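### Only controls carry a Warm Compress Log, and nothing requires it to be handed over before the masked assessor's exams

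*Combined protocol and SAP*

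**What the plan says.** Section 7 states that subjects cannot be masked and that the staff who perform endpoint assessments will be. Section 9.7 gives those staff the visual acuity, slit lamp, TBUT, staining, gland secretion, intraocular pressure and adverse event assessments. It bars them from randomizing, treating, expressing glands and supervising the in-office compress. It wants one person per subject throughout: "the study staff member who performs the baseline assessments should also perform the follow-up assessments".

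The log belongs to one arm. Section 9.5.5 gives it to control subjects, and Appendix B tells them to bring it to every follow-up visit. The reminder call in 9.6.1 asks subjects to bring unused lubricant vials and, "if they are in the warm compress group, their Warm Compress Log".

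On handling the log, the documents say three things:
- Section 9.7: "The study coordinator should collect the Warm Compress Log from the subject".
- Section 9.6.1, after the numbered exam sequence: "The following activities can be performed in any order", with "Collection of Warm Compress Log" on that list beside medication use and the vial count.
- Section 9.6.1, at the end of the visit: control subjects receive a new log.

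Separately, 9.6.1 has the coordinator open the visit by reminding the subject to "not reveal their randomization group to the study personnel who will be performing the follow-up exams".

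**The concern.** The log marks its holder as a control. If collection may come at any point in the visit, it may come after the assessor has finished, and the subject then sits through the exams with a document that states the allocation. Nothing need be said for the assessor to learn the arm.

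TBUT, staining and gland scores are all read by that assessor. TBUT at 1 month is the primary endpoint. Section 12.5.6 re-tests TBUT at 3 and 6 months and relies explicitly on assessor masking through month 6. An assessor who knows the arm could, without intending to, read these outcomes in favor of the device. The symptom questionnaires are not affected by this route, because unmasked subjects complete them themselves.

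**Working it through.** The plan contains no figure on masking, so there is none to reproduce. The check is a comparison of the sections on four questions.

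1. **Does the item identify the arm?** Yes. Sections 9.5.5 and 9.6.1 and Appendix B give the log to controls only. Of the three any-order activities it is the only one specific to an arm. The reminder call asks for vials without distinguishing arms, and the medication instructions in Appendix A (21.1) list nothing that separates them.

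2. **Is the item present at the visits that matter?** By instruction, yes. Appendix B asks for it at each follow-up visit, which includes 1 month. The number of subjects concerned follows from section 12.7: 100 controls randomized, or 100 × (1 − 0.10) = 90 after the planned 10% dropout. That is how many could carry a log to the primary visit, not how many would show one. The route should close after month 6, when section 12.5.8 has controls cross over.

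3. **Who takes the log, and when?** Who: the coordinator (9.7). When: any time (9.6.1). The two sections are compatible, and together they still leave the time open. A coordinator who collects the log after the last exam complies with both.

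4. **Does another rule close the gap?**
   - The opening reminder concerns the subject revealing the group. It does not mention the log.
   - The bar on assessors taking part in treatment controls what they do, not what the subject brings into the room.
   - Section 13 lists masking procedures as a site-initiation training topic but does not give their content.
   - The new log is already issued at the end of the visit, so only the returned log is unprotected.

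On size: if an assessor sees the log at a fraction q of control exams and then reads TBUT lower by b seconds on average, the between-arm difference is inflated by q × b. The documents give neither q nor b, and either could be zero. No value is put on the product.

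**The case against.** The best defense is that the plan already has most of what is needed. The log is kept off the assessor's task list, the coordinator sees the subject first and gives the masking reminder, and sites are trained on masking. The any-order list is there because some tests interfere with others; it was not written as permission to show the log to anyone. A sensible coordinator would take the log at the start. All of this stands, and it makes exposure less likely. It does not supply the missing requirement, since late collection still complies with the text.

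A reader might also infer more than the documents support:

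- **That the assessor handles the log or finds it on the chart.** Collection is the coordinator's job, and no section puts the log among the assessor's papers.
- **That lid signs on Day 1 unmask the TearCare arm.** Section 10.2 lists "Burn, erythema, or swelling of the eyelids", but that list pools events from dry eye itself, the device, the study tests and warm compresses with lid massage. It is not split by arm and does not say that signs last until the next day. Table 3, which sets the Day 1 exams, is not in the text available for review, so a Day 1 slit lamp exam is itself an inference. Giving that exam to an unmasked clinician would also unmask a safety assessment while leaving the assessor face to face with the subject for visual acuity.
- **That the medication review should move as well.** No route from it to the arm is described.
- **That the bias can be stated in seconds.** Any such number would only restate assumed inputs.

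**Conclusion.** The point holds as a gap in sequencing. Sections 9.6.1 and 9.7 together allow a control subject to carry an arm-identifying document through the masked exams, and no other rule in the readable text prevents it. The conclusion rests on two readings: that any order means any order relative to the exams, and that the reminder not to reveal the group does not extend to the log. It does not show that assessors will learn the arm, and it supports no estimate of bias. The change is worth making because the assessor's mask is the only one in the trial and the primary endpoint depends on it.

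**What to change.** In section 9.6.1, take log collection off the any-order list and put it in the opening step, alongside the reminder. Suggested wording: at the start of each follow-up visit, before any masked assessment and out of the Masked Assessor's sight, the coordinator collects the log from subjects who have one; a new log is issued only after all masked assessments at that visit are complete. The second clause makes explicit what the end-of-visit instruction already implies. Section 9.7 can point to this step where it names the coordinator as collector.

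The same person does the same task at the same visit, only earlier. Sample size, alpha, power and the analysis are unchanged. The cost is a sentence in the protocol and a line in the site masking training.

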9.7 MASKED ASSESSOR

To reduce potential bias in the study, study staff performing endpoint assessments will be masked as to the subject's treatment arm. In addition, to ensure consistency in performing the endpoint assessments the study staff member who performs the baseline assessments should also perform the follow-up assessments. An alternate Masked Assessor may be appointed to handle scheduling conflicts, but every effort should be made to have the same person performing all endpoint assessments throughout the study. The Masked Assessor should not perform the randomization, inoffice TearCare Treatment, gland expression or the in-office warm compress treatment prior to home use. Masking will be maintained until all subjects at the site have passed the 6-month follow up time.

The following assessments must be performed by Masked Assessor:

- Manifest refraction and BCVA
- Slit lamp exam
- Tear Break-up Time
- Corneal and conjunctival staining
- Meibomian gland secretion scoring
- IOP
- AE assessment

The study coordinator should collect the Warm Compress Log from the subject.

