6.2 SAFETY ENDPOINTS

Safety will be assessed by evaluating the following measures over time:

- Device-related adverse events (all adverse events will be recorded)
- Best corrected visual acuity (ETDRS)
- Intraocular pressure (IOP)
- Discomfort/pain during treatment

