7 STUDY DESIGN

This is a prospective, randomized, controlled, single-masked, multi-center treatment study. This is a post-market study intended to collect data to update the indication for use for the TearCare System. To reduce potential bias in the study, study staff performing the endpoint assessments will be masked as to the subject's treatment arm. Subjects cannot be masked as it will be obvious to them which treatment they are receiving.

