9.5 BASELINE VISIT

9.5.1 SCHEDULING THE BASELINE VISIT

The baseline visit may be performed over two separate visits. If the visit is performed over two visits, then all baseline exams and questionnaires (Section 9.5.2) and randomization (Section 9.5.3) should be performed in the first visit. If the subject is randomized to the warm compress and lid massage group, the treatment for warm compress and lid massage (Section 9.5.5), and the associated discomfort/pain questionnaire and AE assessment should be performed at the first visit. If the subject is randomized to TearCare, then the TearCare procedure (Section 9.5.4) and the associated Discomfort/pain questionnaire and AE assessment may be performed on a separate visit, as long as it is performed within 7 days of the first visit. If the TearCare procedure is performed on a second visit, then the date of the second visit will be Day 0 of the study for scheduling purposes.

Endpoint assessments performed during the Baseline visit must be performed by the Masked Assessor (See Section 9.7).

Since dry eye drops and lubricants can affect the endpoint assessments, instruct subjects not to use any of these products within 2 hours of the Baseline visit.

[figure not shown]

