12.5.6 EVALUATION OF TREATMENT DURATION

If the primary endpoint is successful at the one month primary time point, then treatment duration will be evaluated using a hierarchical testing procedure. Using data that are obtained at the 3- and 6-month follow-up visits we will again test the primary hypothesis comparing change from baseline Tear Break-Up Time (TBUT) between the treatment and control. We will use the same linear mixed effects (LME) model as in the primary analysis, evaluating each time point separately. The two time points will be tested sequentially, stopping at 3 months if the test fails at that point. Treatment duration will be the maximum time point at which this treatment duration testing succeeds, either 1, 3, or 6 months.

This analysis will not be carried out if the primary 1-month endpoint fails, it is not intended to establish primary effectiveness in the event of study failure at one month.

Note that this analysis will be carried out using data that will be at least partially obtained after the primary database lock. However every effort will be made to maintain the masking of assessors through the 6-month follow-up as described in section 9.7.

This analysis does not affect the type I error for the primary endpoint. The 1- 3- and 6-month TBUT outcomes will likely be highly correlated, however the sequential testing will appropriately control the time-wise type I error rate.

For each secondary endpoint that is successful at the one month time point using the hierarchical testing procedure described in 12.5.5, treatment duration will be evaluated at the 3- and 6-month follow up. Evaluation of treatment duration for the secondary endpoints will be based on sequential testing of 3- and 6-month follow up times separately, in the same manner as for the primary endpoint. Secondary endpoints that fail at the 1-month time point will not be evaluated for treatment duration.

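### Minor: the readable text of 9.7 gives AE assessment to the Masked Assessor without exempting the optional TearCare-only second baseline visit, where doing it would reveal the arm

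*Combined protocol and SAP*

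**What the plan says.** Section 7 explains why the masking of assessors matters: "Subjects cannot be masked as it will be obvious to them which treatment they are receiving". The staff who perform endpoint assessments are masked instead.

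Section 9.7 sets the rules for them.

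- On duration: "Masking will be maintained until all subjects at the site have passed the 6-month follow up time".
- On continuity: "the study staff member who performs the baseline assessments should also perform the follow-up assessments". An alternate may stand in when schedules clash.
- On tasks: "The following assessments must be performed by Masked Assessor", followed by a list that runs from refraction to IOP and ends with AE assessment. The list is not limited to particular visits.
- On exclusions: the assessor is kept from carrying out randomization, the TearCare treatment, gland expression and the in-office warm compress session.

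Section 9.5.1 lets the baseline visit be split. For TearCare subjects, the procedure and "the associated Discomfort/pain questionnaire and AE assessment may be performed on a separate visit", within 7 days of the first. For warm compress subjects, treatment and the AE assessment that goes with it belong to the first visit. The same section refers to 9.7 for endpoint assessments at baseline. If the TearCare procedure takes place at a second visit, that date becomes Day 0.

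**The concern.** A second baseline visit can occur only in the TearCare arm, so anyone who knowingly assesses a subject there knows the arm. The readable text assigns one task at that visit, AE assessment, to the person who must not know it.

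The same person normally goes on to read TBUT at 1 month, which is the primary endpoint. Section 12.5.6 relies on assessor masking again for the 3- and 6-month duration tests, promising that "every effort will be made to maintain the masking of assessors through the 6-month follow-up". Because subjects know their treatment, the masked assessor is the stated protection for these readings. Any loss by this route would fall on the TearCare arm only.

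**Working it through.** No arithmetic applies. The question is whether the provisions can all be followed for one subject, so they are set side by side.

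1. **Who can have a second baseline visit?** Only a TearCare subject (9.5.1). The control arm's treatment and AE assessment are placed at the first visit.
2. **Does an AE assessment take place there?** Yes, when the split is used: 9.5.1 lets it move with the procedure.
3. **Who does it?** On the readable text, the Masked Assessor (9.7 list). No visit is exempted, and 9.5.1 itself points to 9.7 for baseline endpoint assessments.
4. **May that person know the arm?** No. Section 9.7 requires masking until every subject at the site has passed 6 months.

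If 1 to 3 are followed literally for a split-visit subject, 4 fails. The readable text does not say which rule gives way.

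Three comparisons show how far this reaches.

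- **Same-day baseline.** Both arms have an AE assessment after their first treatment, so the task alone does not identify the arm. Section 9.5.3 asks for the assigned procedures immediately after randomization, so same-day treatment is the default and the split is the exception.
- **Split 6-month visit (9.6.2).** Only the TearCare procedure and the discomfort questionnaire may move to the second visit. AE assessment stays at the first, and this conflict does not arise. Only the baseline provision moves it.
- **The exclusions in 9.7.** They stop the assessor from delivering randomization or treatment. They do not mention an AE assessment afterwards, so they do not settle the matter.

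**What cannot be checked.** Section 9.5.2, the procedure steps of 9.5.4 and Table 3 are not readable in the public copy. Any of them may name who does the treatment-session AE assessment.

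**What cannot be sized.** The documents give neither the expected share of split visits nor the effect on a TBUT reading of knowing the arm. Any figure would rest wholly on invented inputs, so none is given.

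**The case against.** The strongest reply is that the list was written for the examination battery and not for the treatment session. It follows the order of the follow-up procedures in 9.6.1 closely. Section 9.5.1 pairs the session AE assessment with the discomfort questionnaire, as part of the procedure. Appendix A repeats the masked-assessor instruction for the eye examinations, whereas 10.3 makes the principal investigator responsible for collecting AE information and 11.6 has the investigator supervise every TearCare treatment. A sensible site could keep the assessor away from the session, and the unreadable 9.5.4 steps may say so. Where an alternate assessor covered the split visit, the usual TBUT reader would not be exposed.

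Much of this stands, and it is why the point is minor. It does not remove the mandatory wording in 9.7. General responsibility for AEs does not cancel that assignment, and an alternate is provided only for scheduling conflicts.

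Stronger readings are tempting, but the documents do not support them:

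- *The protocol instructs sites to unmask the assessor.* It does not. It states two rules that clash in one optional situation.
- *AEs are a safety endpoint in 6.2, so they must fall to the Masked Assessor.* Discomfort or pain during treatment is also a 6.2 endpoint and is not on the 9.7 list. Only the list item assigns the task.
- *The 1-month TBUT comparison is biased by a material share of the planned difference, or its error rate is inflated.* Neither input needed for such a statement is in the documents.
- *The plan fails to name the assessor.* That can be said only of the readable text.

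**Conclusion.** The point holds as a minor inconsistency between 9.7 and 9.5.1. In the readable text, a site that used the split baseline and followed the task list would reveal the TearCare arm to the person who normally reads the 1-month TBUT.

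The conclusion rests on three conditions: the split is used, the site applies the list literally, and no unreadable section already assigns the task elsewhere. Frequency and effect on TBUT are unknown, and no magnitude is claimed. It is still worth correcting because a stated obligation works against the trial's stated protection against bias, and the correction is very cheap.

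**What to change.** State in 9.7, with a cross-reference in 9.5.1, that:

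1. the AE assessment tied to the baseline treatment session, whether same-day or at a separate visit, is done by unmasked treating staff or the supervising investigator;
2. the Masked Assessor does not attend that session;
3. the Masked Assessor is not told whether a second baseline visit took place.

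Keep AE assessment at follow-up visits with the Masked Assessor, in its 9.6.1 position after the eye examinations. If 9.5.2, 9.5.4 or Table 3 already names who does the session assessment, only reconcile the 9.7 list with it.

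The cost is a few sentences and a line in the masking part of site initiation training (Section 13). No staff or visits are added, because the investigator already supervises each TearCare treatment.

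There are two drawbacks. The treatment-session AE assessment becomes unmasked. The fix is also not complete protection: Day 0 moves to the second visit, so a longer gap between the baseline examinations and the Day 1 visit may still hint at the arm.
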